3.1.4 Timing

Patients must be enrolled before taking the first dose of *LBP* or placebo. Participants may be enrolled up to 14 days prior to the planned start of the conditioning regimen and *LBP* or placebo administration.

All clinical and laboratory studies to determine eligibility must be performed within 7 days prior to enrollment unless otherwise indicated in the eligibility section below.

3.1.5 Randomization

Randomization will occur at the time of enrollment. Randomization will take place through the OPEN system. Upon enrollment, sites will receive notification of the kit number of study product that should be dispensed to the patient. All personnel at the site will remain blinded.

3.2 Patient Inclusion Eligibility Criteria

Important note: The eligibility criteria listed below are interpreted literally and cannot be waived. All clinical and laboratory data required for determining eligibility of a patient enrolled on this trial must be available in the patient's medical/research record which will serve as the source document for verification at the time of audit.

All Clinical and Laboratory studies, if applicable, must be obtained within 21 days prior to start of protocol therapy (repeat if necessary). Protocol therapy must begin within 6 months of study enrollment.

See [Section 7.1](#) for required studies to be obtained prior to starting protocol therapy.

3.2.1 Age

Patient must be ≥ 2 years of age and ≤ 25 years of age at time of enrollment.

3.2.2 Diagnosis

Patient must have a diagnosis that is managed with an alternative donor allogeneic hematopoietic cell transplant.

3.2.3 Performance Level

Patients must have a Lansky (for patients ≤ 16 years of age) or Karnofsky (for patients > 16 years of age) performance status score of ≥ 70 . Patients who are unable to walk because of a chronic underlying condition (such as paralysis), but who are up in a wheelchair, will be considered ambulatory for the purpose of assessing performance score. See https://members.childrensoncologygroup.org/prot/reference_materials.asp under Standard Sections for Protocols.

3.2.4 Hematopoietic Cell Transplant (HCT)

Patient must be receiving cells from alternative donor defined as one of the following:

- Unrelated donor with a complete HLA match or a 1 or 2 HLA mismatch, considering only HLA-A, HLA-B, HLA-C, and HLA-DRB1.
- Related donor with a 1 or more HLA mismatch (including haplo-identical).

Note: *history of HCT or other cellular therapy (e.g., CAR-T cells, donor lymphocyte infusions) is permitted.*

3.3 Exclusion Criteria

3.3.1 Patient plans on receiving stem cells from a matched (8/8) related donor.

3.3.2 Patient has used a probiotic dietary supplement within 30 days prior to enrollment. (Consumption of yogurt products is allowed.)

3.3.3 Patient has a history of severe GI tract insult including but not limited to previous bowel perforation, Grade 4 neutropenic colitis or typhlitis, inflammatory bowel syndrome, short small bowel syndrome (Crohn's disease, ulcerative colitis), history of gastrointestinal GVHD, or history of bowel resection.

- 3.3.4 Patient has a medical, psychiatric or social issue that would compromise patient safety or compliance with protocol therapy, or interfere with consent, study participation, follow up, or interpretation of study results.
- 3.3.5 Female patients who are pregnant are not eligible. Women of childbearing potential require a negative pregnancy test prior to enrollment.
- 3.3.6 Patient has diarrhea at the time of enrollment which is *Clostridium difficile* toxin positive.
- 3.3.7 Patient is receiving antibiotic therapy for an active bacterial infection.
- 3.3.8 Patient is allergic to all third or fourth generation cephalosporins, carbapenems, and all aminoglycosides, which are used to empirically treat LBP bacteremia.

3.4 Regulatory Requirements

- 3.4.1 All patients and/or their parents or legal guardians must sign a written informed consent.
- 3.4.2 All institutional, FDA, and NCI requirements for human studies must be met.

4.0 TREATMENT PLAN

Timing of protocol therapy administration, response assessment studies, and surgical interventions are based on schedules derived from the experimental design or on established standards of care. Minor unavoidable departures (up to 72 hours) from protocol directed therapy and/or disease evaluations (and up to 1 week for surgery) for valid clinical, patient and family logistical, or facility, procedure and/or anesthesia scheduling issues are acceptable per COG administrative Policy 5.14 (except where explicitly prohibited within the protocol).

4.1 Overview of Treatment Plan

This will be a double-blind, randomized, placebo-controlled, intervention study that will equally allocate 454 children to either *LBP* or placebo for approximately two months. All patients, patient caregivers, direct healthcare providers, pharmacy and the institutional study team will be blinded to the randomization allocation. Sites will receive notification of the study product kit number to dispense to the patient via email at OPEN enrollment submission. The patient should receive the same study product kit number throughout the study. Study participants will receive a course of either *LBP* or placebo for approximately 64 days, starting at the initiation of conditioning regimen and ending at Day 56. However, participants will be followed until Day 120 to ensure capturing development of aGvHD. The table below provides a study overview.

	Start of conditioning	Day 0 (Graft Infusion)	Day 7	Day 14	Day 28 or discharge	Day 56	Day 120
Study Product Administration (LBP or placebo)	●—————●						
Specimen Collection	-Blood -Stool	-Blood -Stool	-Blood -Stool	-Blood -Stool	-Blood -Stool	-Blood -Stool	-Stool

Please see [Section 7.1](#) for specimen requirements.

4.2 LBP or Placebo Administration

4.2.1 Administration Schedule

Dosing will begin on the first day of the transplant conditioning regimen and continue through day 56 post HCT. The LBP/Placebo does not necessarily need to be given prior to receiving the first dose of the conditioning therapy as long as it starts on that first day. The first day of the transplant conditioning regimen is defined as the first day of chemotherapy or TBI, excluding any preceding anti T-lymphocyte antibody therapy.

4.2.2 Dosing and Administration Guidelines

Dose: The dose used in the study is 1 x 10⁸ colony forming units (CFU)/kg/day. Patients will ingest 1 to 9 mL of reconstituted (mixed solution) *LBP* or placebo once each day. Please refer to the dosing chart below. All doses should be calculated based on the body weight at the start of the conditioning regimen. This should be the weight performed on the day of admission for HSCT (±72 hours). There will be no dose adjustment for weight gain or loss during the course of treatment.

See protocol [Section 6.1.5](#) and the Pharmacy Manual (*available on the COG protocol web page*) for complete and current preparation instructions. The *LBP/Placebo* is supplied in capsules that must be opened and the contents mixed into the volume of liquid specified in the Pharmacy Manual. Once mixed, it is referred to as the “Mixed Solution” for administration as per the chart below.

Study Product Dosing Chart	
Subject's Weight (kg)*	Total Amount of Mixed Solution to be Administered (mL)
≤ 16 kg	1 mL
17-27 kg	2 mL
28-38 kg	3 mL
39-49 kg	4 mL
50-61 kg	5 mL
62-72 kg	6 mL
73-83 kg	7 mL
84-94 kg	8 mL
≥ 95 kg	9 mL

* Subject's Weight should be rounded to the nearest whole kilogram and total mixed solution selected accordingly. Any decimal < 0.5 round down, any decimal ≥ 0.5 round up. For example: a weight of 16.5 kg would be rounded up to 17 kg and 2 mL dose selected as per the Dosing Chart above.

- Patients may receive *LBP* or placebo orally or through a nasojunal, nasogastric or gastrostomy tube. (Please note, an NJ, NG or G tube should not be placed solely for the administration of *LBP* or placebo.)
- Patient should ingest the dose of *LBP* or placebo within 30 minutes of mixing.
- *LBP* or placebo can be taken at any time during the day with or without cold or room temperature food.
- Liquids warmer than 98°F (36°C) are not allowed for mixing the product as high temperature may kill the bacteria.
- If vomiting occurs within 30 minutes of taking the dose, the dose may be repeated once on the same day.
- If a dose is missed, it should be taken immediately and only if there are at least 12 hours until the next scheduled dose. If there are less than 12 hours until the next dose, wait until the next scheduled dose.
- If several doses are missed due to inability to tolerate oral administration (e.g. mucositis or nausea/vomiting), therapy should resume as soon as the patient is able to tolerate oral administration. Please ensure all missed doses are documented in the patient medical record if the patient is in the hospital or patient diary (*available on the COG protocol web page*) if the patient is being treated at home.

Most patients will receive the *LPB* or placebo in both the inpatient and outpatient settings. Adherence to the prescribed regimen will be measured by examination of medication administration records and as documented in the electronic medical record or other hospital source documentation. Patients will be given a diary to document the doses they take at home, which includes instructions for preparation and storage.

Adherence will be defined as administration of at least 80% of the prescribed doses. In the home setting, medication will be dispensed for a specified time period and medication diaries will be completed by families and delivered to the institution on a weekly basis at the time of weekly visits.

4.2.3 Discontinuation due to positive blood culture for LBP

Patients with a blood culture positive for *LBP* at any time during the study will discontinue the study agent (*LBP* or placebo) immediately and the patient will be removed from protocol therapy. *LBP*-bacteremia will be considered an **unexpected severe adverse event** and must be reported within 24 hours through the CTEP-AERS system. See [Section 11.0](#) for reporting requirements.

For patients who test positive for *LBP* in the blood, empiric treatment should begin with either a third- or fourth-generation cephalosporin or carbapenem. If the clinical condition worsens after 24 hours, consideration should be given to adding an aminoglycoside. Empiric therapy should continue until sensitivity results are available. Prompt consultation with an Infectious Disease Specialist is recommended.

4.3 Concomitant Therapy

4.3.1 Supplementation with any additional probiotic dietary supplements is not permitted (food containing live cultures like yogurt is allowed) through Day 120.

4.3.2 Prophylactic use of both broad-spectrum and narrow-spectrum antibiotics is permitted. Information regarding antimicrobial therapy (agent, start and stop times, indication for use) will be collected throughout the study time period.

5.0 EMERGENCY UNBLINDING

Only in the event of a serious adverse event wherein the investigator feels that the patient cannot be adequately treated without knowing the identity of the study medication may the medication code be broken for a particular patient. If emergency un-blinding is required, the patient must stop taking the *LBP* or placebo and be removed from protocol therapy. The treating physician or their designee should use the contact information provided below to obtain the patient's un-blinded treatment information.

Emergency Unblinding Instructions

During normal business hours (9am-5pm Pacific Time)

Please submit unblinding requests using the procedure below:

1. Email to BOTH of the following:
 - a. [contact]
 - b. Research Coordinator email listed on COG protocol webpage
2. Use email subject line: "ACCL1633 – Requesting treatment unblinding"
3. Provide the following info in the body of the email:
 - a. COG Patient ID
 - b. Treatment Assignment (Kit Number)
 - c. Email address for site investigator
 - d. Phone contact for any follow up questions/response to requesting institution

COG Contact Information

- Study Research Coordinator – Contact information listed on the COG Protocol Webpage
- COG Operations Office main line – [contact]

After hours

Please contact the Investigational Drug Service at the Perelman School of Medicine, University of Pennsylvania – Emergency [contact]. Be sure to provide a callback number.

When calling, be ready to provide (1) COG patient ID (2) patient's treatment assignment (kit number) and (3) investigator's callback information.

COG Operations or the Investigational Drug Service located at the Perelman School of Medicine, University of Pennsylvania, will contact the site investigator to provide the patient's unblinded treatment information.

Emergency Unblinding CRF

Once unblinded treatment assignment has been received, complete the Emergency Unblinding CRF in iMedidata Rave by accessing the patient's main page in Rave and using the Add Event dropdown.

6.0 AGENT INFORMATION

6.1 [Redacted] (04/15/2021)

[Redacted]

[Redacted]

[Redacted]

[Redacted]

[Redacted]

[Redacted]

[Redacted]

[Redacted]

[Redacted]

[Redacted]

[Redacted]

[Redacted]

[Redacted]

[Redacted]

[Redacted]

[Redacted]

[Redacted]

[Redacted]

[Redacted]

[Redacted]

[Redacted]

[Redacted]

[REDACTED]

6.1.2

[REDACTED]

[REDACTED]

[REDACTED]

[REDACTED]

[REDACTED]

[REDACTED]

[REDACTED]	[REDACTED]
[REDACTED]	[REDACTED]
[REDACTED]	[REDACTED]
[REDACTED]	[REDACTED]
[REDACTED]	[REDACTED]
[REDACTED]	[REDACTED]

6.1.3 [REDACTED]

[REDACTED]

6.1.4 [REDACTED]

6.1.5

[REDACTED]

[REDACTED]

[REDACTED]

[REDACTED]

[REDACTED]

[REDACTED]

[REDACTED]

[REDACTED]

7.0 EVALUATIONS/MATERIAL AND DATA TO BE ACCESSIONED

Timing of protocol therapy administration, response assessment studies, and surgical interventions are based on schedules derived from the experimental design or on established standards of care. Minor unavoidable departures (up to 72 hours) from protocol directed therapy and/or disease evaluations (and up to 1 week for surgery) for valid clinical, patient and family logistical, or facility, procedure and/or anesthesia scheduling issues are acceptable per COG administrative Policy 5.14 (except where explicitly prohibited within the protocol).

7.1 Required Clinical and Laboratory Evaluations

Studies	Eligibility [§]	First day of conditioning ^{@.&}	Day 0 (Graft Infusion)	Day 7	Day 14	Day 28 or Discharge [%]	Day 56	Day 120
History	X	----	----	----	----	----	----	----
Physical examination, evaluation of GvHD	X	X	X	X	X	X	X	X
Performance status	X	----	----	----	----	----	----	----
Pregnancy test*	X	----	----	----	----	----	----	----
Screening for Clostridium difficile (only if diarrhea at enrollment or first day of conditioning)	X	X ^{&}	----	----	----	----	----	----
Review of LBP administration/patient diary	----	----	X	X	X	X	X	
Blood sample for citrulline and cytokine studies See Section 7.4.1	----	X [^]	X	X	X	X	X ^{a,b}	
Stool sample for correlative studies See Section 7.4.2	----	X [^]	X	X	X	X	X ^b	X ^b

§ All clinical and laboratory studies to determine eligibility must be performed within 7 days prior to enrollment/randomization unless otherwise indicated.

^ Specimen collection on first day of conditioning or anytime within 72 hours before the start of conditioning (prior to chemotherapy). See [Section 7.4.1](#) and [Section 7.4.2](#) for overview of procedures and a Specimen Collection Manual available on the COG protocol web page with further technical detail.

@ The first day of the transplant conditioning regimen is defined as the first day of chemotherapy or TBI, excluding any preceding anti T-lymphocyte antibody therapy. See [Section 4.2.1](#).

% Day 28 or day of discharge, whichever comes first.

* Women of childbearing potential, defined as a female who has had her first menstrual cycle.

& If the patient has diarrhea on the first day of conditioning and repeat stool culture shows *C. diff*, then the patient is ineligible and must be removed from protocol therapy. Reminder: patient condition(s) prior to initiation of protocol therapy must be within parameters required for eligibility. (See [Section 8.1](#))

a Citrulline sample only.

b Blood and stool specimens may be collected within 14 days of the designated time point without being considered a protocol deviation.

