2.5 Preliminary Data

2.5.1 Biomarkers of Intestinal Integrity

Plasma citrulline is a plasma biomarker of intestinal integrity in adults undergoing HCT and in pediatric conditions.⁵⁷⁻⁶¹ To determine the association of plasma citrulline and intestinal integrity in children undergoing alternative donor alloHCT, we measured plasma citrulline levels in 10 children and adolescents beginning at the start of conditioning therapy and then every three to seven days.⁶² The mean citrulline value prior to the initiation of treatment was 20.1 ± 7 μmol/L. The greatest decrease in mean plasma citrulline occurred between the initiation of conditioning and the day of hematopoietic graft infusion (Day 0, 7.1 ± 4.9 μmol/L) and reached a maximal mean nadir at Day 7 (6.6 ± 5.3 μmol/L). Levels did not begin to recover to pre-transplant levels until Day 21 (10 ± 3.7 μmol/L). Significant associations were found between plasma citrulline levels and the odds of developing mucositis (OR = 0.88, 95% CI=0.79–0.99, *p*=0.036) and diarrhea (OR=0.70, CI=0.59–0.84, *p*<0.0001). These results lend further support that plasma citrulline is a marker of GI integrity following alternative donor alloHCT. Moreover, we have identified a therapeutic window in which an intervention may prevent the decline in GI integrity as measured by plasma citrulline levels during HCT.

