7.4 Specimen Collection, Processing and Shipping

7.4.1 Blood Specimens (Citrulline and Cytokines)

Sample Time Points:
	
 • First day of conditioning or anytime within 72 hours before the start of conditioning (prior to chemotherapy) • Day 0 (graft infusion) • Day 7 • Day 14 • Day 28 or discharge, whichever is first • Day 56 (citrulline only) 
Sample acquisition can occur within 72 hours before the first day of conditioning. Sampling can occur within 24 hours before or after designated collection times for D0, D7, D14, D28 without being considered a protocol deviation. D56 sampling can occur within 14 days without being considered a deviation.
								

Blood Collection Procedure:
	
Draw 6 mL of whole blood in a red top tube (supplied by site).
								

Specimen Processing:
	
 1. After collection, allow blood to coagulate at room temperature. 2. After coagulation (but within 1 hour after collection) centrifuge the blood samples at 4°C for 15 minutes at 3000 rpm. 3. Aliquot the serum (upper layer) into three 1.5 mL cryovials (0.5 mL of serum per aliquot). 4. Store frozen at -80°C (or -70°C) immediately after aliquoting. 								

Specimen Labeling:
	
Freezer-safe labels will be provided in specimen kits and must be used as specified in the Specimen Collection Manual. Each cryovial must be legibly labeled with: ACCL1633, COG Patient ID, Timepoint + Aliquot ID (to track individual vials), and Collection Date.
								

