The citrulline levels at each of the time points will be summarized and described by arm. The mean quantitative change in citrulline level from start of conditioning to each of the four later time points will be compared between the 2 arms to determine if *LBP* administration maintains citrulline level via two-sample t-test and repeated-measures general linear modeling which include adjustments for potential confounders. In such analyses, multiple comparison adjustments for the 4 parallel analyses (linear contrasts) will be performed with Bonferroni adjustment to maintain an overall fixed α level. Linear mixed models, which include data from all time points for longitudinal data analyses with adjustment for within-patient correlation, will also be considered.

Likewise, we will compare the incidence of MBIs between two groups looking at the time from start of protocol treatment to first infection as the primary endpoint. Patients without infection will be censored when they meet criteria to be off study. Cox proportional hazards regression will be used to compare the incidence density of infection for the two groups adjusted for confounders (use of total body irradiation, duration of broad spectrum antibiotic usage, incidence of *C. difficile* infection, and duration of total parenteral nutrition). Main analyses for this aim will be based on a modified intention-to-treat principle (inevaluable patients will be excluded), but additional as-treated analysis, subset analysis, or sensitivity analysis may be performed if we observe issues with adherence to the randomized treatment on the study.

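### The Day 28 blood sample is drawn at discharge if that is earlier but analysed as a fixed time point, so an arm difference in discharge timing can distort the citrulline and cytokine comparisons

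*Combined protocol and SAP*

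**What the plan says.** **Sampling.** The footnote to the table in section 7.1 sets the visit at "Day 28 or day of discharge, whichever comes first". Section 7.4.1 repeats the rule for the citrulline and cytokine blood: "Day 28 or discharge, whichever is first". Days 0, 7, 14 and 28 otherwise have a tolerance of 24 hours either way. For the last citrulline draw, "D56 sampling can occur within 14 days without being considered a deviation". Day 56 blood is for citrulline only. Each vial label carries the collection date.

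**Analysis.** For Exploratory Aim 2, section 9.3 states: "The mean quantitative change in citrulline level from start of conditioning to each of the four later time points will be compared" between the arms. The methods are "two-sample t-test and repeated-measures general linear modeling which include adjustments for potential confounders". It adds: "Linear mixed models, which include data from all time points for longitudinal data analyses with adjustment for within-patient correlation, will also be considered". No time scale is given for that model. Exploratory Aim 5 (cytokines) takes over the same approach. Nothing says how a sample taken at an early discharge is to be handled.

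**Background.** Section 2.5.1 reports mean citrulline in 10 children: 20.1 (SD 7) before treatment, 6.6 (SD 5.3) at Day 7 and 10 (SD 3.7) micromol/L at Day 21, with the remark "Levels did not begin to recover to pre-transplant levels until Day 21". Section 7.3.1 predicts an earlier rebound on LBP. Sections 1.2.7 and 9.3 make hospital days an exploratory outcome.

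**The concern.** Of the blood draws up to Day 28, this is the only one whose date is set by an event after randomisation that treatment might influence. The t-test and the repeated-measures model treat every value in that column as belonging to one time point.

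Citrulline is expected to be climbing back at this stage. If LBP patients go home sooner, their sample comes from an earlier and lower part of the recovery curve. A true benefit would then look smaller, although faster recovery is what the aim hopes to show. If the arms differed the other way, LBP could appear better with no marker effect at all. The cytokine comparison has the same structure.

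**Working it through.** **1. The plan's own figure.** Section 9.4 uses two-sided alpha 0.0125 = 0.05/4 and calls the sample sufficient for 0.4 SD (227 per arm) or 0.7 SD (60 per arm) with 80% sampled. That is 0.8 x 227 = 181 and 0.8 x 60 = 48 per arm. The noncentral t gives power of 90% and 81%, so the statement is fair.

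**2. Slope (assumption).** (10 - 6.6)/(21 - 7) = 0.243 micromol/L per day. This is a straight line through two means from 10 children, extended to the period between discharge and Day 28. The documents give no Day 28 value.

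**3. SD of change (assumption on correlation).** The analysed variable is change from start of conditioning, so the scale is the SD of change. The Day 21 SD stands in for Day 28:

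SD of change = sqrt(7² + 3.7² - 2 x r x 7 x 3.7)

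- r = 0: sqrt(62.69) = 7.9
- r = 0.5: sqrt(36.79) = 6.1
- r = 0.8: sqrt(21.25) = 4.6

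**4. Shift.** Shift = slope x gap in mean sampling day. The documents give no discharge distribution, so the gap is assumed: 3 x 0.243 = 0.73 and 5 x 0.243 = 1.21 micromol/L.

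**5. Consequence.** Noncentral t, 181 per arm, alpha 0.0125. The last column assumes a true benefit of 0.4 SD, with LBP sampled earlier, so the effect tested is 0.4 minus the shift.

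| Gap (days) | r | Shift in SD of change | False-positive rate, no true effect | Power for a true 0.4 SD |
|---|---|---|---|---|
| 0 | any | 0 | 1.25% | 90% |
| 3 | 0 | 0.09 | 5% | 66% |
| 3 | 0.5 | 0.12 | 9% | 56% |
| 3 | 0.8 | 0.16 | 16% | 42% |
| 5 | 0 | 0.15 | 15% | 44% |
| 5 | 0.5 | 0.20 | 27% | 27% |
| 5 | 0.8 | 0.26 | 50% | 11% |

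With 48 per arm and no true effect, the false-positive rate is 2%-4% for a 3-day gap and 4%-11% for a 5-day gap.

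**6. Does using the actual day help?** A simulation with 181 per arm and no true effect set the sampling day to the earlier of Day 28 and an assumed discharge day (normal, SD 8 days, not before Day 14). It used slopes of 0.24 and 0.29 per day (the latter if levels regain 20.1 by Day 56: (20.1 - 10)/35) and residual SDs of 3.7 and 7.0. Arm means of discharge 3 to 5 days apart produced sampling gaps of 1.5-2.7 days. The unadjusted t-test then rejected in 2.5%-27.5% of 2,000 runs. Adding the actual day as a covariate gave 0.9%-1.9%, near the nominal 1.25%. The simulated trend depends on calendar day alone, so this does not show that adjustment suffices when discharge also tracks recovery.

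**7. Counting the contrasts.** Citrulline has five post-baseline draws (Days 0, 7, 14, 28 or discharge, 56), but section 9.3 and the Bonferroni step count four. Which draw is left out is not stated. The cytokines have exactly four, including the Day 28 or discharge sample.

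**The case against.** Several points on the other side stand.

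- **The gap is undocumented.** Anyone still in hospital at Day 28 adds nothing to it. If half are (assumed), a 5-day mean gap needs a 10-day gap among the rest.
- **Hospital days.** A reader might infer from Aim 7 that the plan predicts earlier discharge on LBP. It only asks whether hospital days are reduced, gives no expected size, and covers 120 days rather than the period before Day 28.
- **The SD.** Dividing by the raw Day 21 SD of 3.7 gives 0.20 and 0.33 SD. That is the smallest SD reported in section 2.5.1, and raw level is not the analysed variable, so those figures should not be used.
- **The slope.** Sections 2.5.1 and 7.3.1 place the start of recovery at about Day 21, so a line from Day 7 need not describe the discharge period.
- **Day 56.** A reader might count the 14-day tolerance as a second source of bias. In a double-blind trial nothing in the documents suggests that it would be used differently by arm, so it adds noise, not an arm difference.
- **Cytokines.** The documents give no time course, so a claim that the bias runs against LBP does not carry over to them.
- **Methods already listed.** Section 9.3 mentions adjustment for confounders and a mixed model. But sampling day is not named among the adjustments, and the mixed model is optional with no time variable, so this does not close the gap.

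**Conclusion.** The concern holds as a conditional one. The stated analysis treats as fixed a sample whose date may depend on discharge, and discharge timing may itself respond to treatment. If the arms differ in discharge before Day 28, the comparison at that visit can mix marker level with sampling day. For citrulline, earlier discharge on LBP would tend to mask a benefit. With assumed gaps of 3 or 5 days, the shift is about 0.09-0.16 or 0.15-0.26 SD of change, against a stated detectable effect of 0.4 SD. This rests on the extended slope, the assumed gap and an assumed correlation of 0 to 0.8. It also presumes that the Day 28 or discharge value is among the four citrulline comparisons, which the plan leaves unclear.

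A reader might infer that the citrulline and cytokine results will be biased. The documents do not support that: with no gap there is no bias, and for the cytokines neither direction nor size can be worked out. Both aims are exploratory and the primary endpoint is untouched. This is a worthwhile clarification, not a major flaw.

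**What to change.** Amend section 9.3 before unblinding; sample collection need not change.

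1. For Exploratory Aims 2 and 5, make the linear mixed model the main analysis, with actual days from infusion (from the recorded collection dates) as the time variable.
2. Estimate arm contrasts from the model at Days 0, 7, 14 and 28 for both citrulline and cytokines, and at Day 56 for citrulline only, since no cytokine blood is drawn then.
3. Reconcile the four citrulline comparisons with the five post-baseline draws, and set the Bonferroni alpha to match: 0.05/4 = 0.0125 for four, or 0.05/5 = 0.01 for five.
4. Add a sensitivity analysis limited to samples taken within 24 hours of Day 28. Discharge also reflects recovery, so modelling the actual day may not remove all the bias. This subset is itself selected on who was still in hospital (or left close to Day 28), so it should be read beside the main result and not in place of it.

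**Cost:** a few lines of wording and slightly more modelling. With five contrasts the alpha is a little stricter; power for 0.4 SD with 181 per arm goes from 90% to 89% (noncentral t).
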